5.2. Statistical Considerations

5.2.1. Statistical Overview

This trial is a prospective, single-arm, open-label, multi-center clinical evaluation of the safety and effectiveness of the ClariFix™ device when used to ablate unwanted tissue in the nose of subjects with chronic rhinitis. Effectiveness will be evaluated by analyzing the 90-day change from baseline in the 4-symptom rTNSS.

5.2.2. Statement of Hypothesis

The statistical null hypothesis is that the mean 90-day within-subject change is zero; there is no effect of the device on rTNSS.

5.2.3. Analysis Populations

The following subject populations will be created:

Safety (Safety): All subjects enrolled who underwent the device procedure, regardless of outcome.

Efficacy: All subjects enrolled who had at least one follow-up evaluation under this protocol.

Per Protocol (PP): A subset of the Efficacy subjects who underwent the device procedure and do not have major protocol deviations.

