2.2. Risks

The study procedure involves transnasal placement of the ClariFix device under endoscopic visualization and use of local anesthesia. In order to minimize risks associated with the study, the procedure will be performed by practicing otolaryngologists experienced in transnasal procedures. Further, subjects with known allergies to local anesthetic agents shall be excluded from participation in the study.

While nasal endoscopy is generally known to be safe, anticipated risks may include, but are not limited to:

- Temporary pain, discomfort or irritation
- Bleeding
- Cerebrospinal fluid (CSF) leak

Similarly, while generally known to be safe, submucosal placement of a needle and delivery of local anesthesia may be additionally associated with the following risks, not limited to:

- Minor bleeding
- Pain with injection
- Facial numbness or tingling
- Sedation
- Tachycardia, nervousness, anxiety
- Lightheadedness, dizziness, confusion,
- Muscular twitching, tremors
- Infection
- Allergic reaction
- Lidocaine or Tetracaine toxicity with overdose
- Visual disturbance
- Vomiting
- Headache
- Tinnitus
- Seizures
- Hypotension, bradycardia
- Unconsciousness
- Respiratory arrest
- Cardiac arrest

In addition, the specific nature of cryosurgery using the ClariFix Device results in a known potential for adverse events related to the cold application, including but not limited to:

- Bleeding
- Crusting and/or tissue sloughing

- Swelling
- Pain/discomfort and/or facial pain
- Sensory alterations (numbness, tingling) in the face/mouth
- Increase in nasal congestion, Intranasal scarring/nasal obstruction
- Headache
- Dry nose
- Ear blockage
- Septal perforation
- Dry eyes, optical changes or orbital damage
- Vasovagal reaction
- Infection

3. Study Protocol

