3.9.1. Pre-Procedure Evaluation

The baseline evaluation will take place on the day of the study procedure. All female subjects of childbearing potential will be asked to take a pregnancy test (urine). If the subject is pregnant,

they will not be considered eligible to participate in the study. If a subject becomes pregnant after the study treatment, during the study follow-up period, the subject shall be withdrawn from the study and will not undergo any further testing. The subject will be asked to rate their nasal symptoms using the rTNSS. If the subject does not meet the minimum symptom score requirement (**Table 1**, Inclusion criterion b), the subject will not be considered eligible to participate in the study.

If all the eligibility criteria are met, and the subject has signed the IRB-approved informed consent document, the subject shall be considered enrolled. The investigator and/or designee will document the subject's medical information on the Baseline CRF. Subjects will also complete the quality of life questionnaire (RQLQ) described in Section 3.11.4. Subjects shall then undergo treatment with the study device.

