3.9.2. Preparation for Procedure

The subject will be positioned in an upright or partially reclined sitting position. The subject will then undergo appropriate local anesthesia procedure, per physician preference. Baseline images of the intended treatment sites will be collected endoscopically whenever possible.

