4.1. Adverse Events

All adverse device effects (ADE) or procedure-related adverse events (AE) will be documented, including Unexpected Adverse Device Effects (UADE). Additionally, all Serious Adverse Events (SAE), regardless of device- and/or procedure-relatedness, and all ENT, head and neck, respiratory, and/or airway related AEs will be documented.

Adverse events (AE), as defined above, will be assessed continuously throughout the study. An adverse event is defined as any untoward medical occurrence in a subject, regardless of whether the event is related to the device or is a known risk.

Each Investigator shall be responsible for determination of the causal relationship of all adverse events from his/her investigational site to the device and/or procedure, as well as any pre-existing conditions. Each Investigator is responsible for monitoring the safety of the subjects enrolled. The Sponsor is responsible for the ongoing safety evaluation of the product(s) across all sites. The Sponsor shall determine whether an adverse event is reportable and will promptly notify all participating investigators and regulatory authorities, as appropriate, of findings that could affect adversely the safety of subjects, impact the conduct of the trial or alter the IRB's approval opinion to continue the trial.

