5.2.5. Endpoint Analyses

In this single arm, open-label study, the focus of the primary efficacy endpoint analysis is on the magnitude and direction of change over 90 days in the 4-symptom rTNSS. The primary safety endpoint analysis is on the incidence of procedure- or device-related SAEs and UADEs over 90 days post-treatment (however, all AEs will be tracked and reported over the entire duration of the study). The statistical methodology is targeted to employ the paired sample t-test and/or its nonparametric equivalent, the Wilcoxon Signed Rank test. The two-tailed α -level is set at 0.05. No imputation of data will be performed.

All safety analyses will be performed on the Safety Population. All efficacy analyses will be performed on both the Efficacy and PP cohorts, as necessary.

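### Could an anaesthetic SAE that stops treatment fall outside the primary safety incidence because the Safety population's device procedure is undefined?

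*Combined protocol and SAP*

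**What the plan says.** Section 5.2.3 defines the Safety population as "All subjects enrolled who underwent the device procedure, regardless of outcome". Section 5.2.5 adds: "All safety analyses will be performed on the Safety Population". The term device procedure occurs only in 5.2.3, for the Safety and Per Protocol sets, and is not defined.

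The primary safety analysis in 5.2.5 is the "incidence of procedure- or device-related SAEs and UADEs over 90 days post-treatment", with the note that "all AEs will be tracked and reported over the entire duration of the study". Section 4.1 separately requires documentation of "all Serious Adverse Events (SAE), regardless of device- and/or procedure-relatedness", and 4.1.4 requires sites to report SAEs to the Sponsor within 24 hours.

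The order of Visit 2 matters. In 3.9.1, once eligibility and consent are in place, "the subject shall be considered enrolled". Section 3.9.2, on preparation, follows: "The subject will then undergo appropriate local anesthesia procedure, per physician preference". The device is first used in 3.9.3. Section 2.2, however, describes the procedure more widely: "The study procedure involves transnasal placement of the ClariFix device under endoscopic visualization and use of local anesthesia".

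On pregnancy, 3.9.1 withdraws a subject who conceives after treatment and ends further testing. Item f of the SAE definition in 4.1.3 covers fetal distress, fetal death and congenital abnormality.

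**The concern.** The endpoint is wider than the population seems to be. It counts procedure-related as well as device-related SAEs, and 2.2 lists seizures, respiratory arrest and cardiac arrest among the risks of local anaesthesia. If the device procedure means only the cryotherapy step, a subject who has such an event before the device is used is enrolled but outside the Safety set. The trial's most serious procedural event could then be on file with the Sponsor and absent from the primary safety incidence.

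The trial is open-label and sets no safety threshold, so the reported count is itself the result. Choosing the meaning of the term after the event is known would be uncomfortable.

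The pregnancy rule raises a similar worry. Fetal outcomes are SAEs and adverse events are to be tracked throughout, yet no contact is described after withdrawal through which a site would learn of them.

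**Working it through.** **Plan's own figure.** The plan gives no sample size or precision target for safety. Its only such figure, 68 evaluable subjects in 5.2.6, concerns efficacy. It reproduces: for a paired t-test with change 1, SD 2.5 and two-sided alpha 0.05, noncentral-t power is 90.2% at 68 and 89.7% at 67. The definition of the Safety set does not affect it.

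**Who is affected.** Only a subject enrolled (3.9.1) and anaesthetised (3.9.2) who never reaches device use (3.9.3). Anaesthetic events in subjects who go on to receive the device are in the set either way. Unilateral treatment is classed as incomplete in 3.9.3 but still followed.

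**The passages side by side.**

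| Source | Favours |
|---|---|
| 2.2: local anaesthesia is part of the study procedure | counting the subject |
| 3.9: anaesthesia sits under the Study Treatment heading | counting |
| Table 2: AE recording starts in the Procedure column | counting, by inference |
| 3.9.2 and 3.9.3: separate headings for preparation and cryotherapy | leaving out |
| 5.2.5: window runs from treatment | leaving out |
| 3.6: target stated as treated subjects | leaving out |

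The Table 2 inference is this. The Pre-Procedure column shares its name with 3.9.1, and its rTNSS and RQLQ marks match that section. Anaesthesia comes later, so it fits best under Procedure. The boundary is not sharp, because endoscopy is also marked Pre-Procedure and 3.9.2 includes baseline endoscopic images.

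**Size if such an event occurs.** Assume 100 enrolled (5.2.6), one procedure-related anaesthetic SAE before device use, and no other related SAE. Limits are exact (Clopper-Pearson) 95%.

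- Left out: 0/99 = 0%. Upper limit = 1 − 0.025^(1/99) = 3.66%.
- Counted: 1/100 = 1.0%. Lower limit = 1 − 0.975^(1/100) = 0.03%. Upper limit = 97.5th percentile of Beta(2, 99) = 5.45%.

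Taking 100 as treated subjects (3.6), the pair is 0/100 (upper limit 3.62%) and 1/101 = 0.99% (0.03% to 5.39%). That case needs 101 enrolled, above the maximum of 100 in the Protocol Summary.

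**Size if no such event occurs.** One untreated, event-free subject moves the result from 0/99 to 0/100, and the upper limit from 3.66% to 3.62%.

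**How likely it is.** The documents give no rate. In the pilot (1.2), all 27 subjects completed bilateral treatment without complications. The exact upper limit for 0/27 is 1 − 0.025^(1/27) = 12.8%, so the pilot neither suggests such events nor excludes them.

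**What depends on the count.** The only hypothesis, in 5.2.2, concerns rTNSS. Section 5.2.4 plans counts and percentages for categorical data. Study termination (6.3) rests on the judgement of the medical monitor or any investigator on the safety data, not on this proportion. The intervals above only illustrate scale.

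**Pregnancy.** Section 3.9.1 ends testing; it does not bar adverse-event reporting. The subject was treated, so she stays in the Safety set, and an event the site learns of remains reportable. With a pregnancy test on the day of the procedure, most fetal outcomes would fall beyond 90 days and so outside the primary window.

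**The case for a change.** The best argument for a change is that the narrow reading has support within 5.2.3 itself. The Per Protocol set is drawn from Efficacy subjects who underwent the device procedure, while Efficacy asks only for enrolment and one follow-up evaluation. The qualifier suggests that an enrolled, followed subject may not have undergone it. *Regardless of outcome* describes what happens after the procedure and does not bring in someone who never had it. The narrow reading would also remove exactly the subjects whose preparatory event was serious enough to stop treatment, and a definition costs one sentence.

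Much of this stands. The term is undefined, the narrow reading is tenable, and a sentence settling it would be harmless. But 0/99 is only one of two readings, and a set of treated subjects with a window running from treatment is also a coherent choice for a device study. More importantly, the event cannot vanish: 4.1 has it documented, 4.1.4 has it reported, 5.2.5 says AEs are reported for the whole study, and 6.3 has an independent medical monitor assess safety data. What stays open is whether one disclosed event enters one fraction.

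On pregnancy, the absence of a stated route for follow-up information also stands, as an unreconciled gap rather than a contradiction.

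**Conclusion.** No change to the plan follows. The undefined term is missing detail that an analyst can settle sensibly: 2.2 supports counting an anaesthetised subject, and a procedure-related SAE before device use would in any case be documented and reported. The difference is one event in about 100, 0/99 against 1/100, with upper limits of 3.66% and 5.45%. It arises only if a serious anaesthetic event occurs after enrolment and the device is then never used. No test, threshold or stopping boundary turns on it, and the efficacy analysis and its 68 evaluable subjects are unaffected.

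The pregnancy passages in 3.9.1, 4.1.3 and 5.2.5 are not reconciled on whether information is still collected after withdrawal. That is a separate, minor point about whole-study reporting. The documents give no pregnancy numbers; the judgement that they are very small is an assumption.

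The conclusion also assumes that SAEs are documented and reported as 4.1 and 4.1.4 require. If a subject were in fact anaesthetised and not treated, the report would need to say so and state how that subject was counted.

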5.2.4. General Analytical Considerations

Continuous data will be summarized using descriptive statistics: n, mean, standard deviation, median, minimum and maximum. Continuous variables that are recorded using approximate values (e.g., $<$ or $>$) will be replaced by the closest exact value for the calculation of summary statistics. Categorical variables will be summarized using frequency counts and percentages. For ordinal-scaled variables, a combination of the above may be employed as appropriate: frequency and percentage of observations within a category and means and standard

deviations of the scores of the categories. For categorical and ordinal variables, percentages will be calculated based on non-missing data.

5.2.5. Endpoint Analyses

In this single arm, open-label study, the focus of the primary efficacy endpoint analysis is on the magnitude and direction of change over 90 days in the 4-symptom rTNSS. The primary safety endpoint analysis is on the incidence of procedure- or device-related SAEs and UADEs over 90 days post-treatment (however, all AEs will be tracked and reported over the entire duration of the study). The statistical methodology is targeted to employ the paired sample t-test and/or its nonparametric equivalent, the Wilcoxon Signed Rank test. The two-tailed α -level is set at 0.05. No imputation of data will be performed.

All safety analyses will be performed on the Safety Population. All efficacy analyses will be performed on both the Efficacy and PP cohorts, as necessary.

5.2.6. Sample Size Estimation and Assumptions

Assuming a two-tailed α -level of 0.05, and a standard deviation of the within-subject changes from baseline of 2.5, 68 evaluable subjects will yield 90% power to detect a one-point change in the 4-symptom rTNSS. To account for possible dropouts and protocol violations, the enrollment target will be a total sample size of N=100.

5.3. Protocol Adherence

The study investigators are responsible for performing the study in compliance with the protocol. Non-adherence to the protocol will be documented as a protocol deviation. A study site with a large number of violations and/or deviations may be terminated from the study at the Sponsor's discretion.

Protocol deviations that may result in significant additional risk to the subject (e.g., enrollment of a subject who does not meet the study criteria), or non-adherence to Good Clinical Practices (GCP) that may impact patient safety (e.g., failure to obtain proper consent prior to performing study procedures) should be reported to the study Sponsor and the IRB, if applicable, within 5 working days of occurrence.

6. Study Management and Quality Control

6.1. Study Data Collection

Source documentation and Case Report Forms (CRFs) will be provided to all participating sites. CRFs may be completed on paper or via electronic data capture. Data will be reviewed by study staff to identify inconsistent or missing data and to ensure compliance with the study protocol.

Investigators will be responsible for the accurate and timely completion of CRFs during the trial.

6.2. Confidentiality

All information and data concerning study subjects will be considered confidential and handled in compliance with all applicable regulations. Only authorized site staff, the study Sponsor or the Sponsor's designee, IRB, and any relevant regulatory agency will have access to these confidential files. All data used in the analysis, reporting and publication of this clinical trial will be maintained without identifiable reference to the subject. Any data that may be published in abstracts, scientific journals, or presented at medical meetings will reference a unique subject code and will not reveal the subject's identity.

6.3. Safety Data Monitoring

The sites' principal investigators will be responsible for reviewing and adjudicating all adverse events occurring at their sites throughout the course of the study. In addition, an independent medical monitor will assess the safety data at appropriate intervals during the course of the study. Based upon the severity and frequency of adverse events, including any SAEs or UADEs, the medical monitor will determine the continuation or termination of the study based on an evaluation of the risks and benefits of the study.

The study will be terminated if, in the opinion of any of the investigators or the medical monitor, the safety data indicates unacceptable risks to study participants. Unacceptable risk will be identified by the occurrence of adverse events that exceed the anticipated level of severity or frequency.

6.4. Investigator Responsibilities

6.4.1. General Responsibilities

Investigators are responsible for ensuring the investigation is conducted according to all signed agreements, the Protocol, and applicable regulations. The investigator must protect the rights, safety, privacy and welfare of the subjects under the Investigator's care. Investigators will assume overall responsibility and accountability for study site staff and for the clinical data obtained during the study.

6.4.2. Investigator Records

The investigator and study staff must maintain attributable, legible, contemporaneous, original and accurate records relating to the conduct of the investigation. Records must be retained for the period of time defined in the clinical research agreement.

These records must be available and suitable for inspection at any time by Sponsor representatives (monitors), the reviewing IRB, or the relevant regulatory agency. The Investigator will supply access to study-related medical records, original laboratory data, and other records and data as they relate to the trial. The investigator will ensure that both he/she and his/her study staff have adequate time and resources to devote to the study, including study enrollment, subject evaluations, study documentation and site monitoring.

Subject Treatment Questionnaire Visit: Upon completion of the Subject Treatment Questionnaire Visit, the documentation of subject consent and questionnaire source documentation will be transferred to the corresponding site for each subject via a certified shipping method (i.e. FedEx).

6.4.3. Investigator Reports

The investigator is responsible for preparation and submission of the following reports:

- Report of any serious adverse events or unanticipated adverse device effects shall be submitted to the Sponsor within 24 hours of knowledge of the event, and full details of the event will be provided no later than 5 working days after the Investigator first learns of the effect.
- Withdrawal of IRB approval of the investigator's part in the investigation shall be reported to the Sponsor within 5 working days.
- Progress reports on the investigation to the sponsor, the monitor, and the reviewing IRB annually. Alternatively, the Sponsor may prepare the report.
- Protocol deviations and violations shall be reported to the Sponsor
- Failure to obtain informed consent prior to use of a device in a subject shall be reported to the Sponsor and IRB within 5 working days after the use occurs

6.4.4. Device Accountability

The investigator is responsible for maintaining records of receipt, use or disposition of all devices. The Sponsor will maintain records of all shipments and disposition of the study devices.

6.5. Sponsor Responsibilities

6.5.1. General Responsibilities:

The Sponsor assumes overall responsibility for the conduct of the study including assurance that the study satisfies applicable regulatory requirements. Arrinex, Inc. assumes all responsibilities per applicable regulations, and shall:

IRB approval: Ensure IRB approval is secured for the investigation prior to enrolling subjects.

Investigators: Select investigators qualified by training and experience. Providing investigators with the information needed to conduct the study properly. Obtain a signed Investigator Agreement from each participating investigator. Study sites will be evaluated to ensure that they have an adequate subject base and can provide sufficient staff and documentation support to conduct the study properly.

Monitoring: Select monitors qualified by training and experience and ensure proper monitoring of the study.

Data Management and analysis: Ensure data collection, verification, analysis, records storage, etc. Sponsor will assist with presentation(s) and/or publication(s).

Device Provision: The Sponsor will provide all study devices to the site. The Sponsor will deliver study devices only to qualified investigators participating in this trial. The Sponsor will not deliver study devices to any site until evidence of IRB approval has been provided to the Sponsor.

6.5.2. Training

Study Training: To ensure uniform data collection and protocol compliance, Sponsor personnel will provide an educational session to study site personnel as needed, which will cover the Protocol, techniques for the identification of eligible subjects, data collection and form completion, and the device directions for use. The investigator and study staff will be trained on the study device and protocol, applicable regulations and requirements, and expectations of the study, enrollment expectations, subject selection, informed consent, required clinical data and record keeping, etc.

Device Use: Representatives of the Sponsor will train investigators in use of the study device.

